### 9.2 ADVERSE EVENTS

#### 9.2.1 Definition of Adverse Event, Adverse Device Effect, Serious Adverse Event and Serious Adverse Device effect according to ISO 14155:

9.2.1.1 **Adverse Event (AE)** is defined as any untoward medical occurrence in a patient or clinical investigation patient.

9.2.1.1.1 This definition does not necessarily imply that there is a causal relationship between the adverse event and the device under investigation.

9.2.1.2 **Adverse Device Effect (ADE)** is defined as any untoward and unintended response to a medical device. This definition includes any event resulting from insufficiencies or inadequacies in the

instructions for use or the deployment of the device. It also includes any event that is a result of a user error.

#### 9.2.1.2.1 **Valve-related adverse events**

Valve-related adverse events will be defined according to the definitions included in the current available guidelines: Akins CW, Miller CD, Marko I, Turina MI, Kouchoukos NT, Blackstone EH, Grunkemeier GL, Takkenberg JJM, David TE, Butchart EG, Adams DH, David M, Shahian DM, Hagl S, Mayer JE, Lytle BW. Guidelines for reporting mortality and morbidity after cardiac valve interventions. EJCTS 33 528 (2008) 523–528.

9.2.1.3 **Serious Adverse Event (SAE)** is defined as an adverse event that:

9.2.1.3.1 Led to death;

9.2.1.3.2 Led to a serious deterioration in the health of a patient that:

- Resulted in a life threatening illness or injury;
- Resulted in a permanent impairment of a body structure or a body function;
- Required in-patient hospitalization or prolongation of existing hospitalization; and
- Resulted in medical or surgical intervention to prevent permanent impairment to a body structure or a body function.

9.2.1.3.3 Led to foetal distress, foetal death or a congenital abnormality or birth defect.

9.2.1.4 **Serious Adverse Device Effect (SADE)** is defined as an adverse device effect that has resulted in any of the consequences characteristic of a serious adverse event or that might have led to any of these consequences if suitable action had not been taken or intervention had not been made or if circumstances had been less opportune.

#### 9.2.2 List of Anticipated Adverse Events and Adverse Device Effects:

The following represents a list of anticipated Adverse Events (AE) and Adverse Device Effects (ADE) experienced in either animal and/or clinical studies to date with aortic valve replacement operations, or reported in instructions for use and literature. Anticipated Adverse Events (AE) and Adverse Device Effects (ADE) include: Angina (chest pain), Cardiac arrhythmias, Bleeding events (including pre-operative bleeds), Death (valve and non-valve related), embolism, endocarditis, explant, heart failure, hemolysis, haemolytic anemia, myocardial infarction, non-structural dysfunction, paravalvular leak, valve regurgitation, reoperation, stroke, structural deterioration, valve thrombosis, valvular pannus.

### 9.2.3 Procedure for Recording and Reporting Adverse Events

- 9.2.3.1 Safety surveillance and reporting will be done for all patients enrolled in the investigation.
- 9.2.3.2 Safety surveillance and reporting starts at the time when the patient is enrolled into the investigation (date of signature of the informed consent) until the last investigational visit has been performed, or the patient has died, or the patient concludes his participation into the study.
  - 9.2.3.2.1 **All Serious Adverse Events and all Adverse Device Effects** are to be documented and reported to the sponsor **immediately**.
  - 9.2.3.2.2 **Non-Serious Adverse Events** documentation and reporting are limited to cardiovascular and neurovascular events.
- 9.2.3.3 Should an AE occur, record AE information in the hospital records, document the information into the Adverse Event case report form (CRF) as soon as possible. By completing the CRF the sponsor will be notified.
  - 9.2.3.3.1 Refer to appendices "Data Collection" and "Data Collection Method".
  - 9.2.3.3.2 Access the eCRF application.
  - 9.2.3.3.3 Select the visit the AE is related to or indicate it as unscheduled visit.
  - 9.2.3.3.4 Enter adverse event information into the **AE Notification** section of the CRF.
    - Date the AE occurred;
    - Date the center investigator or delegate became aware of the AE;
    - Main complaints/symptoms of the AE;
    - Initial diagnosis of the AE;
    - Potential cause of the AE;
    - Pre-existing medical conditions related to the AE;
    - Seriousness of the AE;
    - Device relationship to AE; and
    - Status of the AE.
  - 9.2.3.3.5 The CRF must be authorized by the principal investigator or delegated co-investigator.
  - 9.2.3.3.6 Submit the CRF. When the CRF is submitted, an alert is generated notifying the sponsor.

9.2.3.3.7 As soon as the final details are available for the adverse event, the information should be reported on the AE Follow-Up section of the CRF.

9.2.3.3.8 Access the eCRF application.

9.2.3.3.9 Edit AE CRF, document information into the **AE Follow-Up** section of the case report form.

- Hospitalization details (if applicable);
- Diagnostic test information (if applicable);
- Treatment given (if applicable);
- Final medical diagnosis & cause;
- Patient condition;
- Final AE status;
- Seriousness of AE based on final medical diagnosis and cause;
- Relationship of AE to device based on final medical diagnosis & cause.

9.2.3.3.10 The CRF must be authorized by the principal investigator or delegated co-investigator.

9.2.3.3.11 Submit the CRF.

9.2.3.4 Additional information will be requested, if necessary, by the Sponsor for reporting of AEs to regulatory authorities.

9.2.3.5 The investigator must notify the EC or IRB, if appropriate, in accordance with national and local laws and regulations.

**NOTE:** If an adverse event is documented at the patient's last follow up visit (10 years), both the notification and follow-up information on the AE CRF are to be provided to the sponsor.

Pre-existing cardiac conditions that require planned hospitalization are not to be considered as AE.

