#### **3.2 SECONDARY OBJECTIVES**

- 3.2.1 The secondary objectives of this investigation are to evaluate valve-related complications in the long-term.

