## **5 PATIENT SELECTION CRITERIA**

### **5.1 PATIENT ENROLLMENT**

A patient who meets all the inclusion criteria and does not meet any of the exclusion criteria is eligible to participate in the investigation. A patient is enrolled in the investigation only when s/he has provided written informed consent. Once enrolled, a patient is expected to comply with the scheduled visits and required activities according to the protocol.

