### **5.2 INCLUSION CRITERIA**

- 5.2.1 Patients implanted for less than 9 months, or candidate for implantation with a St Jude Medical Trifecta valve, as per current guidelines;
- 5.2.2 Patient requires aortic valve replacement. (Note: patients undergoing concomitant procedures, e.g. coronary artery bypass grafting, supracoronary replacement of ascending aorta, mitral valve repair, tricuspid valve repair, atrial fibrillation ablation, patients that had previous aortic valve replacement or CABGs are eligible for this study).
- 5.2.3 Patient is legal age in host country.
- 5.2.4 Patients must be able and willing to provide written informed consent to participate in this investigation; and
- 5.2.5 Patients must be willing and able to comply with all follow-up requirements.

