## 9 PROTOCOL DESCRIPTION

### 9.1 PROTOCOL PROCEDURES - OVERVIEW

Table 1 – Protocol Procedure Overview

These activities are applicable to all patients.

(\*) This is only when available

(\*\*) This is **only to be performed when applicable.**

	When	Window	Activities
Pre-Intervention		Not Applicable	
 
• Patient Eligibility
 
• Patient Informed Consent
 
• Patient Demographics & Physical Examination
 
• Patient Cardiovascular History
 
• Patient Current Cardiac Medications
 
• Patient Medical History
 
• Echo (*)
 

Intervention (+baseline)		Not Applicable	
 
• Aortic Valve Replacement Information
 
• Operative Information
 
• Adverse Events(**)
 
• Echo (*)
 

Pre-discharge		Not Applicable	
 
• Patient Current Cardiac Medications
 
• Adverse Events(**)
 
• Echo (*)
 

Yearly follow-up	Yearly	<30 days >61 days	
 
• Patient Current Cardiac Medications
 
• Adverse Events (**)
 
• Echo (*)
 

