## 9.9 PROTOCOL REQUIRED FOLLOW-UP

- 9.9.1 Scheduled visits will occur yearly over 10 years after the implant date. The follow up will occur in the outpatient department of each participating institution or, if not possible, by telephone contact with the patient.
- 9.9.2 The Follow Up schedule is summarized in Table 1.
- 9.9.3 The following information will be collected at the follow up visit either from hospital records or through patient interaction (documented in the hospital records):
  - 9.9.3.1 Provide the most recent value (within the last month) of the New York Heart Association (NYHA) classification;
  - 9.9.3.2 Patient Cardiac Current Medication
    - Provide information on cardiac medication therapy.;
  - 9.9.3.3 Echocardiography (if available)
    - Provide follow-up echo data (echo date must be in the follow-up window);
- 9.9.4 Record the follow up information in the hospital records and complete the Follow Up Case Report Form (CRF).
- 9.9.5 Adverse Event (when applicable)
  - 9.9.5.1 Check with the patient if any adverse events or adverse device effect occurred since the last visit and document this in the hospital records.
  - 9.9.5.2 Report the adverse event according to specifications in section "Adverse Event" of the Case Report Form (CRF).
- 9.9.6 Patient Death (when applicable)
  - 9.9.6.1 If the patient died before the visit took place, report it immediately to the sponsor as indicated in section "Patient Death".
- 9.9.7 Early Withdrawal (when applicable)
  - 9.9.7.1 If the patient decides to withdraw from the investigation for whatever reason, report this immediately to the sponsor as indicated in section "Early conclusion to patient participation".
- 9.9.8 Refer to "Appendix Data Collection" for access and information regarding patient data collected for this investigation.

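### Adverse-event surveillance starts at consent, so for patients enrolled after implant the non-fatal events before consent fall outside required reporting, while other sections can be read as asking for them

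*Combined protocol and SAP*

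**What the plan says.** - **Who may enter.** Inclusion criterion 5.2.1 covers "Patients implanted for less than 9 months, or candidate for implantation with a St Jude Medical Trifecta valve". Section 5.1 fixes the moment of enrolment: "A patient is enrolled in the investigation only when s/he has provided written informed consent".
- **When surveillance starts.** Section 9.2.3.2: "Safety surveillance and reporting starts at the time when the patient is enrolled into the investigation (date of signature of the informed consent". Section 9.3.1.2 repeats this start for deaths.
- **What Table 1 asks for.** Table 1 (section 9.1) states "These activities are applicable to all patients" and lists adverse events at Intervention, Pre-discharge and each yearly visit. Its footnote marks the adverse-event item as "only to be performed when applicable".
- **What the visit sections ask for.** Section 9.7.3.1 has the site check at baseline for any event and gives no start date. Section 9.8.3.1 looks back to the previous visit at pre-discharge, and 9.9.5.1 does so at follow-up: "Check with the patient if any adverse events or adverse device effect occurred since the last visit". All three sit under a when-applicable heading.
- **Sources and timing.** Sections 9.7.2 and 9.8.1 let baseline and pre-discharge data come from hospital records. Section 9.7.1 places baseline activities after enrolment and within the 30 days before surgery.
- **Time origin.** Section 8.2.1 counts time from implant for reoperation due to SVD. Section 9.9.1 schedules visits from implant. Section 8.3.1 covers other time-to-event data in general terms and names no origin.
- **Objective.** Section 3.2.1 is to "evaluate valve-related complications in the long-term".

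**The concern.** Take a patient who consents eight months after surgery. Under 9.2.3.2 the operation, the hospital stay and the next eight months all precede surveillance. A bleed, an embolism or a resolved endocarditis in that time need not be reported. A site that works from Table 1 and 9.7.3 could reasonably report the same events, and both sites could claim to be following the protocol.

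What is at stake is the early part of the complication profile. If late entrants are counted as at risk from implant while their pre-consent events are not collected, those months enter the analysis as event-free. The resulting error runs in one direction, in favour of the valve, and its size depends on how many patients enter late and on how each site reads the rule.

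**Working it through.** **Step 1. The sections side by side, for a patient enrolled after implant**

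| Section | Effect for this patient |
|---|---|
| 5.2.1 with 5.1 | Eligible; enrolled only at consent, up to just under 9 months after implant |
| 9.2.3.2 | Required reporting starts at consent |
| Table 1, Intervention and Pre-discharge | Adverse events listed for every patient, when applicable; both periods precede consent |
| 9.7.3.1 | Any event, no start date |
| 9.8.3.1, 9.9.5.1 | Since the previous visit, which for this patient may lie before consent |
| 9.7.1 | Cannot be met: baseline must follow enrolment and precede surgery |

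No section requires events between implant and consent to be collected retrospectively, and none says what *when applicable* means for this group. Section 9.7.1 suggests that the visit sections were written for patients enrolled before surgery.

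**Step 2. Inputs for the size**

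- Number of patients: 801 (6.3.1 and 8.1.3). The stated figure follows from 641/0.8 = 801.25.
- Entry window: 9 months = 0.75 years (5.2.1).
- Mortality: 63.4% at year 10 (8.1.2).
- Assumed, because the documents do not give them: the late-entrant share f, a consent delay uniform over 0-9 months (mean 4.5 months = 0.375 years), and no retrospective capture.

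**Step 3. Person-time**

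- First 9 months, ignoring deaths: 801 × 0.75 = 601 patient-years.
- Ten years, ignoring deaths: 801 × 10 = 8,010 patient-years.
- Ten years with exponential mortality fitted to 63.4%: the rate is −ln(0.366)/10 = 0.1005 per year, so 801 × 0.634/0.1005 ≈ 5,050 patient-years.
- Unobserved: f × 801 × 0.375.

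**Step 4. Share of events missed**

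An event at month t in a late entrant is missed if consent comes later, with probability 1 − t/9.

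- Constant hazard over 0-9 months: f × 0.5.
- Events spread evenly over the first month: f × (1 − 0.5/9) = f × 0.944.
- In-hospital events (t close to 0): approximately f.

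| f | Unobserved patient-years | Missed, 0-9 months | Missed, first month | Share of 8,010 | Share of 5,050 |
|---|---|---|---|---|---|
| 25% | 75 | 12.5% | 23.6% | 0.9% | 1.5% |
| 50% | 150 | 25% | 47.2% | 1.9% | 3.0% |
| 75% | 225 | 37.5% | 70.8% | 2.8% | 4.5% |

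At f = 10% the constant-hazard figure for 0-9 months is 5%.

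The missed share equals the understatement of the rate only if the denominator runs from implant. If complication time starts at consent, the unobserved months leave the denominator too. That bias then disappears, and the cost is fewer patients informing the early period.

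**The case against.** The case against has real weight.

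- **Endpoints.** The three named secondary endpoints in 4.2.1 are survival, freedom from valve-related death and freedom from SVD. None counts embolism, bleeding, endocarditis, leak, thrombosis or haemolysis. Non-fatal events cannot move the first two. This stands: objective 3.2.1 is the main hook, and its own wording is about the long term.
- **Table 1.** A reader might infer a flat contradiction with 9.2.3.2. The text does not go that far, because the adverse-event items in Table 1, 9.7.3, 9.8.3 and 9.9.5 are all qualified as when applicable. What remains is an unresolved conflict for late entrants, since the qualifier is never explained for them.
- **Certainty of loss.** A reader might also infer that every pre-consent event is lost. The documents do not support that. Hospital records may be used, 9.7.3.1 sets no start date, the adverse-event form records the date of occurrence separately from the date of awareness, and a persisting condition may be found after consent. The protocol also refers to data-collection appendices that are not in the public text and might contain a look-back rule. Permission to use records does not, however, override an explicit start date.
- **Time origin.** Implant is stated as the origin only for SVD reoperation. For complications, counting from implant is an assumption, though nothing in the plan specifies delayed entry.
- **Late-entrant shares.** The 25% to 75% range has no source in the documents, and 9.7.1 presumes enrolment before surgery. The figures are illustrations.
- **Site differences.** No between-site comparison is planned, so uneven collection matters for the pooled early rates and not for a site contrast.

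**Conclusion.** The point holds as a gap in a stated rule. Followed as written, 9.2.3.2 leaves non-fatal events between implant and consent outside required reporting for patients admitted under the post-implant arm of 5.2.1, and the rest of the protocol does not settle whether they should be collected.

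The exposure is in early valve-related complication rates. These would be understated by about 13%, 25% or 38% over 0-9 months at late-entrant shares of 25%, 50% or 75%, and by up to the full late-entrant share for in-hospital events. The figures assume uniform consent delay, constant hazard (for the 0-9 month figures), no retrospective capture and time counted from implant. With partial capture or time counted from consent, the understatement is smaller or absent.

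A reader might carry these percentages over to the 10-year results or to the primary endpoint. That is not supported. The same unobserved time is about 1% to 3% of 10-year patient-years before deaths, or about 1.5% to 4.5% under the plan's mortality. The effect on 10-year freedom from SVD reoperation is probably small, and the sample size is unaffected. Deaths before consent are a separate matter of survivor selection, because those patients cannot enrol. This is a worthwhile, inexpensive correction and does not threaten the main analysis.

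**What to change.** **Collection.** Amend 9.2.3.2 so that, for patients enrolled after implant, valve-related adverse events, serious adverse events, adverse device effects and reoperations from the implant date to consent are recorded at enrolment from hospital records and patient interview. Each should carry its true onset date and a retrospective flag. Immediate reporting to the sponsor would apply from consent onward.

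**Alignment.** Bring 9.7.1, 9.7.3, 9.8.3 and Table 1 into line, and say what *when applicable* means for this group.

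**Analysis.** State the time origin for complications. Where a patient's records are unavailable, count complication time from consent (delayed entry). State that look-back person-time is conditional on survival to consent, for example by reporting patients enrolled before and after implant separately.

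**Cost.** One clause, one flag on the adverse-event form and modest chart work at sites that already extract operative and discharge data for these patients. The consent wording must cover data back to implant. Reported early complication rates will probably be slightly higher. Delayed entry alone, without the look-back, would remove the denominator bias more cheaply but would leave early rates resting on fewer patients.

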## 9.3 Patient Death

### 9.3.1 Procedure for Recording and Reporting Patient Death

9.3.1.1 Safety surveillance and reporting will be done for all patients enrolled in the investigation.

9.3.1.2 Safety surveillance and reporting starts at the time when the patient is enrolled into the investigation (date of signature of the informed consent) until the last investigational visit has been performed.

9.3.1.2.1 All **Patient Deaths** are to be documented and reported to the sponsor **immediately**.

9.3.1.3 Should death occur, record death information in the hospital records, **immediately** document the information in the Death case report form (CRF). By completing the CRF the sponsor will be notified.

9.3.1.3.1 Refer to appendices "Data Collection" and "Data Collection Method".

9.3.1.3.2 Access the eCRF application.

9.3.1.3.3 Select the visit the patient death is related to or indicate it as visit unscheduled visit.

9.3.1.3.4 Enter patient death information into the Patient Death CRF.

- Date the death occurred;
- Date the center investigator or delegate became aware of the death;
- Place where death occurred (e.g. hospital, nursing home, patient's home);
- If death was witnessed;
- If autopsy was performed;
- If the Trifecta Valve was returned to SJM? If not, reason should be specified.
- Temporal cause of death
- Primary cause of death including if death was caused by valve-related complications (hemolysis, bleeding event, structural valve deterioration, endocarditis, non-structural dysfunction, valve reoperation, embolism, sudden unexplained, valve thrombosis)
- Details regarding death; and
- If details of serious adverse event associated to the death are known by the center/investigator/delegate.

9.3.1.3.5 The CRF must be authorized by the principal investigator or delegated co-investigator.

9.3.1.3.6 Submit the CRF. When the CRF is submitted, an alert is generated notifying the sponsor.

- 9.3.1.4 Patient death may be an outcome of a serious adverse event (SAE). If the death is related to a SAE, all the efforts to get SAE details should be made and the Adverse Event CRF must be completed.
- 9.3.1.5 Patient death is an early conclusion to the patient's participation in the investigation. Complete Termination CRF.
- 9.3.1.6 The investigator must notify the EC or IRB, if appropriate, in accordance with national and local laws and regulations.

## 9.4 EARLY CONCLUSION TO PATIENT PARTICIPATION

- 9.4.1 All reasonable efforts should be made to retain the patient in the clinical investigation until completion of the clinical investigation.
- 9.4.2 If a patient concludes their participation in the investigation, the patient's future medical care will not be influenced by this decision, whether it is voluntary or otherwise,
  - 9.4.2.1 A patient/family member may request to withdraw from the investigation at any time; She/he would be able to do so without having to justify it and without affecting her/his relationship with the investigator.
  - 9.4.2.2 An investigator may withdraw a patient from the investigation at any time if she/he thinks it is in the patient's best interest; or
  - 9.4.2.3 An investigator may withdraw a patient, if the patient does not come for their scheduled visits and/or is not compliant with the regimen of the protocol. This patient will be considered "lost to follow-up"; A patient will be considered "lost to follow-up" when 3 attempts to contact the patient were unsuccessful: A minimum of 2 documented phone calls by a physician/delegate to the patient/emergency contact and a certified letter sent to the last known address.
  - 9.4.2.4 The Investigation is temporarily stopped or terminated, either at the local, national or international level, at the request of Ethics Committees, Competent Authorities, Departments of Health or the investigational Sponsor.
  - 9.4.2.5 A patient dies. Refer to section 9.3, "Patient Death";
- 9.4.3 Should a patient withdraw and conclude participation in the investigation, document the information in the Termination case report form (CRF) as soon as possible. By completing the CRF the sponsor will be notified.
  - 9.4.3.1 Refer to appendices "Data Collection" and "Data Collection Method".
  - 9.4.3.2 Access the eCRF application.

- 9.4.3.3 Select the visit the patient death is related to or indicate it as visit unscheduled visit.
- 9.4.3.4 Enter patient early conclusion information into the Termination CRF.
  - Date the early conclusion occurred; and
  - Reason for the early conclusion;
- 9.4.4 The CRF must be authorized by the principal investigator or delegated co-investigator.
- 9.4.5 Submit the CRF. When the CRF is submitted, an alert is generated notifying the sponsor.

